7 DATA MONITORING COMMITTEE AND OTHER EXTERNAL COMMITTEES

Not applicable.

8 STATISTICAL CONSIDERATIONS

8.1 Sample Size Determination

This is an estimation study, without statistical testing, and hence there are no power considerations.

It is expected that response rate for the primary endpoint for all five arms will be somewhere around 80%. With this response rate, and 40 subjects per arm, an exact 95% confidence interval would run from roughly 64% to 91%.

8.2 Populations for Analyses

The following definitions are used in this document:

- Enrolled subjects:** Subject who signed an informed consent form and were assigned a Patient Identification number (PID);

- Randomized subjects: Enrolled subjects who received a treatment assignment from the IVRS;
- Treated subjects: Randomized subjects who received at least 1 dose of BMS-955176 or TDF. (Also referred to as the mITT analysis set)

8.3 Endpoints

8.3.1 Primary Endpoint(s) Stage 1 and Stage 2

The primary endpoint for Stage 1 and Stage 2 is the proportion of subjects with plasma HIV-1 RNA < 40 c/mL at Week 24. This will be assessed with the FDA snapshot algorithm. This uses the last on-treatment plasma HIV-1 RNA measurement, within an FDA-specified visit window, to determine response.

8.3.2 Secondary Endpoint(s)

- The antiviral efficacy will be determined by the proportion of subjects with plasma HIV-1 RNA < 40 c/mL at Weeks 48 and 96 using the FDA snapshot algorithm
- The antiviral efficacy will also be assessed by the proportion of subjects with plasma HIV-1 RNA < 200 c/mL at Weeks 24, 48 and 96 using the FDA snapshot algorithm approach with positive response defined as HIV-1 RNA < 200 c/mL
- The emergence of HIV drug resistance among samples sent for drug resistance testing will be assessed using the most recent version of the IAS-USA list of HIV-1 drug resistance mutations
- Changes from baseline in \log_{10} HIV-1 RNA and in CD4+ T-cell counts, and changes in the percentage of CD4+ T-cells will be assessed using on-treatment laboratory results, and pre-specified visit windows
- The frequency of SAEs and AEs leading to discontinuation (DC) will be tabulated directly from the case report forms (CRFs). The summary will count the number of subjects that have at least one event
- The occurrence of new AIDS defining events (CDC Class C events) will be tabulated from the CRFs. The summary will count the number of subjects that have at least one event
- The steady-state plasma PK of BMS-955176 will be assessed using the intensive PK data, collected at Week 2 from a subset of subjects

8.4 Analyses

In general, categorical variables are tabulated with counts and percents. Continuous variables are summarized with univariate statistics (eg, mean, median, standard error).

Longitudinal analyses use pre-defined visit week windows. Unless otherwise specified, windows around planned measurement times are constructed based on the midpoint between planned study visits (ie, half the duration of time between study visits), and data are summarized at each scheduled visit.

For the calculation of descriptive statistics of observed data, subjects must have a baseline measurement to be evaluable for longitudinal tabulations of parameter values and changes from baseline.

Tabulations of the following endpoints present the number of unique subjects with an event: protocol deviations; interruptions of study therapy; non-study medications; adverse events; and laboratory abnormalities. Thus, multiple occurrences of the same event are counted only once per subject.

8.4.1 Demographics and Baseline Characteristics

The following demographic and baseline characteristics will be summarized by treatment arm and overall using the treated subjects:

- Demographics: age, race, ethnicity, gender, geographic region;
- Disease characteristics at baseline: plasma HIV-1 RNA level, CD4+ T-cell counts and percentages, CD8+ T-cell counts, HIV-1 subtype;
- Laboratory tests at baseline;
- Pre-treatment CDC Class C AIDS events;
- Prior medications

8.4.2 Efficacy Analyses

The efficacy analyses will be based on the treated subjects.

8.4.2.1 Primary Efficacy Analyses

The primary efficacy endpoint is the proportion of subjects with plasma HIV-1 RNA < 40 c/mL at the Week 24 snapshot within each stage. This endpoint is assessed with the FDA snapshot algorithm. The primary analysis will be based on a modified ITT (mITT) approach. A sensitivity analysis will be conducted using an observed values approach. The two approaches will be implemented as follows:

- Modified ITT: The numerator will be based on subjects with plasma HIV-1 RNA < 40 c/mL at Week 24. The denominator will be based on all treated subjects
- Observed values: Similar to the mITT approach, the numerator will be based on subjects with plasma HIV-1 RNA < 40 c/mL at Week 24. However, the denominator will be based on the treated subjects with plasma HIV-1 RNA at Week 24

Response rates will be tabulated by treatment arm (within the stage) with exact binomial 95% confidence intervals.

Subgroup summaries will be provided to examine the impact of baseline viral load and HIV-1 Clade (Clade AE versus Other) for both the mITT and the observed values approach. Other subgroup summaries may be provided to examine the impact of other important covariates such as CD4+ count, sex, geographic region, etc

8.4.2.2 Secondary Efficacy Analyses

The following secondary endpoints will be summarized by treatment arm:

- Proportion of subjects with HIV-1 RNA < 40 c/mL at Week 48 and Week 96 using mITT and observed values
- Proportion of subjects with HIV-1 RNA < 200 c/mL at Week 24, 48 and 96 using mITT and observed values
- Change from baseline in \log_{10} HIV-1 RNA and in CD4+ T-cell counts, and changes in the percentage of CD4+ T-cells over time
- Newly emergent genotypic substitutions (using all on-treatment isolates) will be tabulated by treatment arm
- The newly emergent phenotypic resistance profile (using all on-treatment isolates) will be tabulated by treatment arm

8.4.3 Safety Analyses

The investigators will determine the intensity of adverse events (AEs) and the relationship of AEs to study therapy. The investigators' terms will be coded and grouped by system organ class using the latest version of the Medical Dictionary for Regulatory Activities (MedDRA) in production at BMS. AEs will be presented by system organ class and preferred term. Presentations will include both non-serious and serious adverse events, unless specified otherwise. If a subject had an adverse event with different intensities over time, then only the greatest intensity will be reported.

Deaths will be listed for enrolled subjects without regard to onset.

In analyses of fasting lipids over time, values will be excluded after the start of serum lipid reducing agents.

The frequency of the following safety events will be summarized by treatment arm for treated subjects:

- SAEs
- AEs leading to discontinuation of study therapy
- AEs by intensity
- CDC Class C AIDS events
- Laboratory abnormalities by toxicity grade

8.4.4 Pharmacokinetic Analyses

The following PK parameters will be summarized by treatment arm:

- C_{max} : maximum observed plasma concentration
- T_{max} : time of maximum observed plasma concentration

- C_{tau} : observed plasma concentration at the end of a dosing interval (eg, concentration at 24 hours)
- C_0 : observed pre-dose plasma concentration
- AUC(TAU) : area under the concentration-time curve in one dosing interval

8.4.4.1 Sparse Pharmacokinetic Analyses

Sparse pharmacokinetic data will be used in population PK, PK/PD and, as available, PK/VK analyses.

8.4.4.2 PK/PD and PK/VK Analyses

PK data obtained from this study will be pooled with data from other studies to perform an integrated population PK analysis, exposure-response analyses for selected safety and efficacy endpoints, and, as available, viral kinetic modeling of BMS-955176 in combination with other ARVs to support the on-going development of BMS-955176. These analyses will facilitate optimal dose selection for future Phase 3 studies.

The population PK, exposure-response, and, as available, viral kinetic analyses, will be reported separately.

8.4.5 Biomarker Analyses

Details about the biomarker analyses will be provided in the Statistical Analysis Plan (SAP).

8.4.6 Outcomes Research Analyses

Details about the outcomes research analyses will be provided in the SAP.

8.4.7 Other Analyses (including Virologic Futility)

An analysis of virologic futility will be performed at Week 24 when the last randomized subject in Stage 1 completes their Week 24 visit. This analysis will be conducted to evaluate whether the BMS-955176 arm shows significantly worse antiviral efficacy (HIV-1 RNA < 40 c/mL using the FDA snapshot algorithm) than the TDF-containing arm. The comparison of Arms 1 (containing BMS-955176) to Arm 2 (containing TDF) will be made with one-sided, Fisher's exact tests, conducted at the 0.01 probability level.

An analysis of virologic futility will be performed at Week 24 when the last randomized subject in Stage 2 completes their Week 24 visit. This analysis will be conducted to evaluate whether a BMS-955176 arm shows significantly worse antiviral efficacy (HIV-1 RNA < 40 c/mL using the FDA snapshot algorithm) than the TDF-containing arm. The comparison of Arms 3-4 (containing BMS-955176) to Arm 5 (containing TDF) will be made with one-sided, Fisher's exact tests, conducted at the 0.01 probability level.

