3 INVESTIGATIONAL PLAN

3.1 Study Design and Duration

This is a randomized, active-controlled, staged, open-label clinical trial. Approximately 200 treatment-experienced HIV-1 subjects will be randomized to one of five treatment arms (approximately 40 per arm) in a staged fashion.

Randomization will be stratified by HIV-1 Clade (AE versus Other). The number of subjects with HIV-1 Clade AE will be capped at a maximum of approximately 3 per treatment arm.

The data from the Week 24 analysis of Stage 1 and AI468038, including safety, efficacy and pharmacokinetics, will be examined to trigger the start of Stage 2 and confirm the two doses of BMS-955176 for study in Stage 2.

Stage 1:

In Stage 1, subjects will be randomly assigned 1:1 to one of two treatment arms and on Day 1 will begin dosing with:

- Arm 1 : BMS-955176 120 mg QD + ATV/r 300/100 mg QD + DTG 50 mg QD, or
- Arm 2: TDF 300 mg QD + ATV/r 300/100 mg QD + DTG 50 mg QD

Stage 2:

In Stage 2, subjects will be randomly assigned 1:1:1 to one of three treatment arms and on Day 1 will begin dosing with:

- Arm 3: BMS-955176 120 mg QD + ATV 400 mg QD + DTG 50 mg QD, or
- Arm 4: BMS-955176 180 mg QD + ATV 400 mg QD + DTG 50 mg QD, or
- Arm 5: TDF 300 mg QD + ATV/r 300/100 mg QD + DTG 50 mg QD

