3.1.2 Day 1/Baseline Visit

3.1.2.1 Day 1/Baseline Visit for Arms 1 and 2 - Stage 1

In Stage 1, approximately 80 subjects will be randomized 1:1 (approximately 40 per arm) to either of the treatment arms containing boosted atazanavir (ATV/r).

On the Day 1 Visit, subjects in Arms 1 and 2 will begin QD dosing with BMS-955176 or TDF, each in combination with ATV/r and DTG (see [Section 4.5](#) for additional details of Selection and Timing of Dose).

- Arm 1 : BMS-955176 120 mg QD + ATV/r 300/100 mg QD + DTG 50 mg QD, or
- Arm 2: TDF 300 mg QD + ATV/r 300/100 mg QD + DTG 50 mg QD

3.1.2.2 Day 1/Baseline Visit for Arms 3, 4 and 5 - Stage 2

In Stage 2, approximately 120 subjects will be randomized 1:1:1 (approximately 40 per arm) to either of the two BMS-955176 treatment arms containing ATV, or to the TDF Arm.

On the Day 1 Visit, subjects will begin QD dosing with BMS-955176 in combination with ATV and DTG, or TDF in combination with ATV/r and DTG (see [Section 4.5](#) for additional details of Selection and Timing of Dose).

- Arm 3: BMS-955176 120 mg QD + ATV 400 mg QD + DTG 50 mg QD, or
- Arm 4: BMS-955176 180 mg QD + ATV 400 mg QD + DTG 50 mg QD, or
- Arm 5: TDF 300 mg QD + ATV/r QD 300/100 mg + DTG 50 mg QD

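### The binding Week 24 futility test is valid but wastes power: about 6 to 7 points to Fisher's discreteness, and up to about 12 more by leaving out baseline HIV-1 RNA

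*Protocol*

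**What the plan says.** Section 8.4.7 asks whether a "BMS-955176 arm shows significantly worse antiviral efficacy (HIV-1 RNA < 40 c/mL using the FDA snapshot algorithm) than the TDF-containing arm" and answers with comparisons that "will be made with one-sided, Fisher's exact tests, conducted at the 0.01 probability level". It applies this to Arm 1 against Arm 2 in Stage 1, and to Arms 3 and 4 against Arm 5 in Stage 2. No covariate or stratum enters.

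These are the only between-arm efficacy tests in the protocol. The primary analysis (Section 8.4.2.1) tabulates response rates by arm with exact confidence intervals. The result is binding: Section 3.1.5.1 ends the trial if Arm 1 meets the criterion, and Section 3.1.5.2 moves a Stage 2 arm that meets it to another dose.

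On baseline information, Section 3.1 states: "Randomization will be stratified by HIV-1 Clade (AE versus Other"), with clade AE capped at about 3 per arm. Section 8.4.2.1 adds: "Subgroup summaries will be provided to examine the impact of baseline viral load and HIV-1 Clade". Baseline HIV-1 RNA is scheduled for every subject and bounded below by the 400 c/mL entry criterion.

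No power is given for the test. Section 8.1 says: "This is an estimation study, without statistical testing, and hence there are no power considerations".

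**The concern.** A test that can end the trial or change an arm's dose should use its 0.01 error allowance and the information already collected. This one appears to do neither. With two arms of 40 the 2x2 table is coarse, so Fisher's conditional test runs well below its nominal level. A baseline value likely to bear on reaching < 40 c/mL is left out.

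The protocol presents the futility analysis as one of its protections against a subtherapeutic regimen (Sections 1.1.1 and 1.5), and Section 7 provides no data monitoring committee. The error at stake is therefore mainly a missed inferior BMS-955176 arm.

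**Working it through.** **Inputs from the protocol.** 40 per arm and 80% expected response (Section 8.1); one-sided 0.01 (Section 8.4.7); at most about 3 clade AE subjects per arm (Section 3.1); baseline RNA of at least 400 c/mL, or 2.6 log10 (Section 3.3.1).

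**Assumed, because the protocol gives no figure.** True BMS-955176 response of 40% to 70%; baseline log10 RNA normal with mean 4.2 and SD 0.8, floored at 2.6; odds ratio (OR) for non-response per log10 RNA of 1 to 4.5.

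**1. The protocol's own figure.** The Clopper-Pearson interval for 32/40 is 64.4% to 90.9%. This agrees with Section 8.1: "With this response rate, and 40 subjects per arm, an exact 95% confidence interval would run from roughly 64% to 91"%.

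**2. Fisher's test, enumerated exactly.** For t responders of 40 on BMS-955176 and c of 40 on control,

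p(t,c) = Σ over k = 0..t of C(40,k)·C(40,t+c−k) / C(80,t+c).

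At c = 32, p is 0.0086 for t = 21 and 0.0153 for t = 22, so futility needs 21/40 or fewer. The rejection probability is

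Σ over t and c of Bin(t; 40, pT)·Bin(c; 40, 0.80)·1{p(t,c) ≤ 0.01}.

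- Size at 80% vs 80%: 0.0053 (maximum over common rates 0.0056).
- Power against 80%: 6% at 70%, 28% at 60%, 45% at 55%, 63% at 50%, 89% at 40%.

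**3. Removing the discreteness, with no covariate.** Boschloo's test orders tables by p(t,c) and takes as its p-value the largest probability, over the common response rate, of a table at least as extreme. At 22/40 vs 32/40 it gives 0.009, so the boundary moves from 21 to 22. Power is 34.9% at 60% (28.0 + 6.9) and 69.0% at 50% (62.6 + 6.4).

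**4. Adjusting for baseline RNA.** A logistic model of response on continuous log10 RNA is fitted without treatment. The statistic is the sum of residuals in the BMS-955176 arm, re-randomised within clade (3 + 3 AE, 37 + 37 Other). There were 2,000 to 2,500 simulated trials per cell, so the Monte Carlo error of a power near 40% is √(0.4 × 0.6 / 2,500), about 1 point. Total gain over Fisher in the same trials, and what remains after subtracting step 3:

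| True rates | OR per log10 | Total gain | Beyond Boschloo |
|---|---|---|---|
| 80% vs 60% | 1 | +6.3 | 6.3 − 6.9 = −0.6 |
| | 1.65 | +7.2 | 7.2 − 6.9 = +0.3 |
| | 2.7 | +10.9 | 10.9 − 6.9 = +4.0 |
| | 4.5 | +16.3 | 16.3 − 6.9 = +9.4 |
| 80% vs 50% | 1 | +6.4 | 6.4 − 6.4 = 0 |
| | 2 | +7.6 | 7.6 − 6.4 = +1.2 |
| | 3 | +13.8 | 13.8 − 6.4 = +7.4 |
| | 4.5 | +17.8 | 17.8 − 6.4 = +11.4 |

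Null rejection at 80% vs 80% was 0.008 to 0.009 (8,000 trials), so the level holds.

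**5. Sensitivity.** With SD 0.6 and OR 4.5 the total gain falls to +11.5 at 60% and +12.7 at 50%. With SD 0.8 it is +3 to +5 at 70%, +3 to +8 at 40%, and +20 at 55% with OR 4.5. An exact test stratified by clade and RNA dichotomised at 4.7 log10 gains only −2 to +5, so the continuous form matters. Stratifying by clade alone changes power by about −1 to 0 points.

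**6. What chance imbalance does to Fisher.** At 80% vs 60% and OR 2.7, one SD of the between-arm mean difference in log10 RNA is 0.8 × √(2/40) = 0.18. Power is 14% when BMS-955176 has the lower baseline by more than that, and 45% when it has the higher, against 28% overall.

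**The case against.** Fisher's test holds its level in a randomised comparison without any covariate. Chance imbalance in viral load is ordinary sampling error, which the 0.01 level already covers. That stands: a reader might infer that the protocol's test is wrong or biased, and nothing in the documents supports it. The issue is efficiency.

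A reader might also credit the whole 6 to 18 point gain to the omitted covariate and stratum. Steps 3 to 5 rule that out: the first 6 to 7 points need no covariate, and clade contributes none. Nor do the documents establish that baseline RNA is strongly prognostic. Section 8.4.2.1 plans only to examine its impact. In the mITT analysis, subjects without a Week 24 value count as non-responders, and such failures need not follow baseline RNA.

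The adjusted test has a real drawback. If RNA is irrelevant, it acts as a tie-breaker. With the counts held fixed and RNA drawn independently of response, against 32/40 on control the adjusted test declared futility in 93% of draws at 21/40, 53% at 22/40 and 15% at 23/40. Boschloo's boundary is fixed.

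Finally, this test is not the only protection. Section 1.1.1 withholds Stage 2 if a subtherapeutic regimen looks likely, and Section 3.5 has individual virologic discontinuation rules. Even at about 35% power, a 20-point deficit is missed about two times in three. These points limit the importance of the gain; they do not remove it.

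**Conclusion.** The concern holds as one of efficiency. Section 8.4.7 fixes a valid test that uses about half of its 0.01 allowance and ignores a baseline value already collected. From protocol inputs alone, true size is about 0.5%. At assumed true rates of 60% and 50%, power is about 28% and 63%, and 6 to 7 points are recoverable without any prognostic assumption. Baseline RNA adds from nothing to about 12 points more at those rates, over an assumed OR per log10 of 1 to 4.5; this upper end is conditional and should be presented so. Re-randomising within clade strata makes the analysis match the randomisation and has no power benefit.

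**What to change.** In Section 8.4.7, for both stages, replace Fisher's test by a prespecified one-sided 0.01 re-randomisation test within clade strata. The statistic is the BMS-955176 arm's sum of residuals from a treatment-free logistic model of Week 24 snapshot response on continuous baseline log10 HIV-1 RNA. Report the unadjusted exact result alongside. If a fixed count boundary is preferred, use Boschloo's test at the same level, which keeps the 6 to 7 points and gives up the covariate gain.

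The cost is protocol and SAP wording and a short program; no new data or subjects are needed. There are three downsides. The false-futility chance rises from about 0.5% to at most the 1% the protocol already accepts. The test is less familiar. With the adjusted version, the same response counts can fall on either side of the boundary depending on baseline RNA.

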3.1.5 Selection of the Continuation Dose of BMS-955176

3.1.5.1 Selection of the Continuation Dose, and the Switch for Stage 1

Once all subjects in Stage 1 have reached Week 24*, BMS will conduct an interim analysis of efficacy, safety, resistance and pharmacokinetics.

As described in [Section 8.4.7](#), an analysis of Virologic Futility will also occur. If Arm 1 meets criteria for Virologic Futility at Week 24, the clinical trial will be terminated.

The Week 24 analysis of Arms 1 and 2, combined with the Week 24 analysis of all Arms in the AI468038 study, will be used to select a Continuation Dose of BMS-955176 for Arm 1 in this study. Subjects in the BMS-955176 Treatment Arm 1 may subsequently be transitioned to a selected Continuation Dose.

Subjects in the Arm containing TDF will continue with the TDF treatment regimen.

The assigned backbone will not change.

The Week 24 efficacy, safety, and pharmacokinetic analyses from Stage 1 and study AI468038 will also trigger the start of Stage 2.

** If the Continuation Dose cannot be clearly identified using the Week 24 data, the study will continue in original fashion until an analysis of the Week 48 data can be performed and the Continuation Dose is selected. If a Continuation Dose cannot be selected based upon the Week 24 data, this does not preclude the ability to start recruitment of Stage 2.*

After the Continuation Dose is selected, and once all of the logistics (eg, distribution of clinical drug supplies, activation of the new portion of the IVRS) have been completed globally, the transition of the subjects in Arm 1 to the Continuation Dose will occur. It is anticipated that this transition will occur on or after all subjects have reached Week 48 (the earliest subjects to begin study treatment could be well beyond Week 48 when the switch to the Continuation Dose occurs).

3.1.5.2 Selection of the Continuation Dose, and the Switch for Stage 2

Once all subjects in Stage 2 have reached Week 24, BMS will conduct an analysis of efficacy, safety, resistance and pharmacokinetics.

As described in Section 8.4.7, an analysis of Virologic Futility will also occur. If a BMS-955176 dose arm meets criteria for Virologic Futility at Week 24, subjects in said arm will begin dosing with the next highest available remaining dose of BMS-955176.

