PHYSICAL EXAMINATION	Physical examination should complement elements obtained from the history. Acutely, the investigator may assess for signs of intravascular volume depletion (eg, orthostasis) and/or aspiration of vomitus as appropriate. Abdominal tenderness and guarding may indicate inflammation. The presence of fecal blood can indicate mucosal damage (eg, from an ulcer). Complete evaluation of dyspepsia should include an oral examination (poor dentition or pharyngeal erythema) and lungs for wheezing. ³⁷
DIAGNOSTIC EVALUATION AND MANAGEMENT	A major goal in the diagnostic evaluation of a subject with upper GI symptoms is to quickly arrive at a final diagnosis without exposing the subject to unnecessary (invasive) testing; Investigators should exercise good clinical judgment ³⁸ in this regard. A major goal of therapy is directed at correcting the underlying identifiable medical or surgical abnormalities. Consultation (eg, gastroenterologist) is recommended as clinically indicated.
Grade 1 symptoms	Subjects may be treated symptomatically. If subjects develop dyspepsia alone, generally only limited and direct diagnostic testing should be performed. ³⁷ If the subject has dyspepsia they should limit alcohol, caffeine, chocolate, tobacco, other contributing concomitant medications (eg, NSAIDs) and eating directly before bedtime. A variety of OTC medications are available to address constipation and diarrhea as indicated. Please refer to Appendix 1 for Prohibited and Precautionary Therapies.
Grade 2 symptoms ^a	Diagnostic testing may include but is not limited to the following (as clinically indicated): 
 • Serum chemistries and assessment of hemoglobin if not recently performed. • Testing for Helicobacter pylori • Serologies (eg, celiac disease) • PCR for viruses (eg, CMV) • Iron panel or Vitamin B12 level 
For subjects who develop dyspepsia or are infected with H. pylori the use of H2 antagonists, PPIs, Sucralfate, and antacids are prohibited (see Appendix 1 Prohibited Medications). If such therapy is required, discontinuation from the trial is necessary. The use of antiemetic's (eg, Prochlorperazine) can be utilized as indicated. Management should be targeted at addressing the underlying pathology.

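### The Stage 2 Virologic Futility rule counts adverse-event exits as non-response, can then move the arm to another dose, and leaves that move undefined for Arm 4 and for both arms flagged

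*Protocol*

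**What the plan says.** The futility test is set in section 8.4.7 of the Protocol (Revised Protocol 01). At Week 24 of Stage 2, Arms 3 and 4 are each compared with Arm 5 to see "whether a BMS-955176 arm shows significantly worse antiviral efficacy (HIV-1 RNA < 40 c/mL using the FDA snapshot algorithm) than the TDF-containing arm", using "one-sided, Fisher's exact tests, conducted at the 0.01 probability level". Stage 1 has the same test for Arm 1 against Arm 2.

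Three other places determine who counts as a responder:

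- Section 8.3.1, on the snapshot: "This uses the last on-treatment plasma HIV-1 RNA measurement, within an FDA-specified visit window, to determine response".
- Section 8.4.2: "The efficacy analyses will be based on the treated subjects".
- Section 8.4.2.1, modified ITT approach: "The denominator will be based on all treated subjects". The observed-values sensitivity analysis differs in that "the denominator will be based on the treated subjects with plasma HIV-1 RNA at Week 24".

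The consequence is in section 3.1.5. In Stage 1, futility in Arm 1 ends the trial. In Stage 2, "subjects in said arm will begin dosing with the next highest available remaining dose of BMS-955176". Section 3.1 lists the Stage 2 BMS-955176 doses as 120 mg (Arm 3) and 180 mg (Arm 4). Section 7 provides for no data monitoring committee.

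**The concern.** The test is introduced in sections 1.1.1 and 1.5 as protection against a subtherapeutic regimen and resistance. What it measures is wider: virologic non-response plus every exit before the Week 24 window, whatever the reason. Section 3.5 requires a subject to stop for any adverse event that the investigator judges to make continuation unwise, and treatment is open-label.

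The Stage 2 action treats a flag as a dose question. If Arm 3 is flagged because subjects left for adverse events, one reading of 3.1.5.2 moves those still on treatment from 120 to 180 mg. The footnote to Table 1.1.2-1 projects steady-state AUC of 35.8 and 69.2 µg·h/mL at these doses with a high-fat meal, a ratio of 69.2/35.8 = 1.9. Section 1.4.1.3 reports that gastrointestinal events in a 180 mg food-effect study occurred only in the fed arms, where exposure was higher. A tolerability signal could thus lead to more exposure.

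The rule is also incomplete. For Arm 4, if the next highest dose means a higher one, the protocol contains none. If it means the highest dose still remaining, the answer would be 120 mg. If both arms are flagged, nothing says which doses remain available.

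**Working it through.** **The plan's own figure.** Section 8.1 gives an exact 95% interval of roughly 64% to 91% for 80% response in 40 subjects. Clopper-Pearson for 32/40 gives 64.4% to 90.9%, so it reproduces. No operating characteristics are stated for the futility test.

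**Inputs from the protocol.** 40 per arm; one-sided Fisher's exact test at 0.01; expected response about 80% in every arm. The denominator of all treated subjects is taken from 8.4.2 and 8.4.2.1, because 8.4.7 does not restate it.

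**Inputs assumed.** Suppression s among subjects who stay, equal in both arms, and drop-out d before the window. The protocol gives neither figure.

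**Smallest flag.** With control at 32/40, an arm is flagged at 21/40 (p = 0.0086) but not at 22/40 (p = 0.0153). If each arm has 8 virologic non-responders and the BMS-955176 arm also loses 11 subjects to adverse events, its count is 40 − 8 − 11 = 21, and it is flagged with no excess of virologic failure. On the observed-values denominator the comparison is 21/29 against 32/40, and p = 0.325.

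**How often.** Response probability is s × (1 − d). The flag probability is the sum, over all pairs of responder counts (t, c), of Bin(t; 40, pT) × Bin(c; 40, pC) where the Fisher p-value is at most 0.01. With 5% control drop-out, pC = 0.90 × 0.95 = 0.855, or 0.80 × 0.95 = 0.76.

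| BMS-955176 drop-out | pT, s = 90% | Flagged | pT, s = 80% | Flagged |
|---|---|---|---|---|
| 5% | 0.855 | 0.4% | 0.76 | 0.5% |
| 10% | 0.81 | 2.0% | 0.72 | 1.6% |
| 15% | 0.765 | 6.0% | 0.68 | 4.0% |
| 20% | 0.72 | 13.9% | 0.64 | 8.4% |
| 30% | 0.63 | 41.3% | 0.56 | 25.9% |
| 40% | 0.54 | 73.0% | 0.48 | 52.2% |

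Virologic effect is equal in every row.

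**Both arms flagged.** Let q(c) be the probability that one arm is flagged given c control responders. The probability that both are flagged is the sum over c of Bin(c; 40, pC) × q(c)². If both arms truly respond at 50% against 80% on control, this is 47%. The undefined case is then close to as likely as not, in just the situation that the rule is meant to handle.

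**The case against.** Several objections have force.

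- **The endpoint is defensible.** Section 8.4.7 says openly that efficacy means snapshot response below 40 c/mL, which is the primary endpoint. A reader might infer that drop-outs are labelled virologic failures. They are not: they are non-responders, and protocol-defined virologic failure is a separate definition in 5.4.1.2.
- **A virologic-failure test would weaken the safeguard.** It is tempting to conclude that the futility endpoint should be replaced. Take control at 90% suppression with 5% drop-out, and a truly inferior arm at 60% suppression with 30% drop-out. The snapshot test fires in 96% of trials. A test of virologic failure on treated denominators fires in 34%. Replacement is not supported.
- **Differential exits are not established.** A reader might take the acid-reducer rule in Table 6.7.1.4-1 ("If such therapy is required, discontinuation from the trial is necessary") as falling mainly on BMS-955176 arms. Appendix 1 bases that ban on ATV and DTG, which all five arms take. Section 1.1.3 expects fewer gastrointestinal effects in Arms 3 and 4, and section 1.5 reports no adverse-event discontinuations in Phase 2a. The food-effect result shows that an excess is possible and gives no rate.
- **The effect needs a large imbalance.** About 11 excess exits in 40 are required in the worked example, and the flag probability is 2% or less at 10% drop-out against 5% on control.
- **Other safeguards exist.** The same Week 24 analysis covers safety, resistance and pharmacokinetics, and a Continuation Dose is chosen afterwards. Even so, 3.1.5.2 states the futility move as something that will happen and does not make it depend on that review.

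One might also say that the 180 mg arm has no workable outcome. That holds under only one reading of the phrase; what the text shows is that the outcome is undefined.

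**Conclusion.** The concern stands in limited form. The Stage 2 test mixes tolerability loss with antiviral failure, and the attached action makes no distinction between them, so a flag on Arm 3 could raise exposure in subjects still on treatment for a non-virologic reason. The chance of this is small at modest drop-out and substantial at large drop-out: 0.4% to 6% for 5% to 15% on BMS-955176, and 14% to 73% for 20% to 40%, given 90% suppression and 5% control drop-out. These rates are assumptions, and the treated-subject denominator is inferred from 8.4.2 and 8.4.2.1. The dose move concerns Stage 2 only; a Stage 1 flag ends the trial.

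The gap in 3.1.5.2 depends on no drop-out assumption. The outcome is ambiguous for Arm 4 and absent when both arms are flagged.

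**What to change.** Keep the snapshot test in 8.4.7. Beside it, specify the same one-sided Fisher comparison on the observed-values denominator that 8.4.2.1 already defines, and a table splitting snapshot non-responders into virologic reasons and no-data or adverse-event reasons. State that all three are read before any action is taken.

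The observed-values comparison should not stand alone, because it leaves out subjects without a Week 24 value. Its use is to show whether a snapshot flag is virologic.

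The sponsor should also reconcile 3.1, 3.1.5.2 and 8.4.7, so that the stated consequence distinguishes virologic from non-virologic flags and has a defined outcome for the highest-dose arm and for both arms flagged. Which dose or clinical rule applies is for the sponsor; none is proposed here.

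The cost is wording in two or three sections and slightly more analysis, with no new data. The futility reading becomes less automatic. The change should be made before any Stage 2 Week 24 data are analysed, and preferably before the Stage 1 Week 24 analysis, which uses the same test.
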